10.4.2 Safety Analyses Set

The safety analysis set will consist of all patients who receive the assigned treatment.

10.5 Statistical Analyses

10.5.1 General Approach

Descriptive statistics will be calculated on all variables by treatment group. Frequencies will be computed for all binary/categorical variables, and continuous variables will be summarized using medians, quartiles, and ranges. Data from schedules may be pooled. Exploratory and post hoc analyses may be conducted at the discretion of the PI.

10.5.2 Analysis of the Primary Endpoint

The primary outcome is the incidence of post-operative delayed gastric emptying using the ISGPS criteria and MAGS grading, coded as yes and no. The rate per group, odds ratio (OR) and the associated 95% confidence intervals (CIs) will be calculated assuming a binomial distribution. The logistic regression model will be considered to investigate the effect of PPIs accounting for the interested variables on the incidence of post-operative delayed gastric emptying. The interested variables include age, gender, body mass index, comorbidities, preoperative proton pump inhibitor usage, and surgical reconstruction method. The relationships between these variables and the endpoint may exist.

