Study Description:	This is a randomized placebo-controlled study of patients who will undergo pancreaticoduodenectomy at Washington University in St. Louis/Barnes-Jewish Hospital. The study aims to determine the impact of administration of Proton Pump Inhibitors (PPIs) on the postoperative course in these patients. Postoperative administration of PPI and no intervention are both considered standard of care approaches.
Objectives:	
Primary Objective: Determine the effect of PPIs on the incidence of delayed gastric emptying within 90 days in patients after pancreaticoduodenectomy.
 
Secondary Objectives:
 
 • Determine the effect of PPIs on the incidence of overall postoperative complications in the patients after pancreaticoduodenectomy. • Determine the marginal ulcer-free survival (MUFS) within 90 days after surgery in the patients undergoing pancreaticoduodenectomy.
Endpoints:	
Primary Endpoint: Incidence of delayed gastric emptying using the ISGPS criteria and MAGS grading.
 
Secondary Endpoints:
 
 • Incidence of surgical complication defined by the Modified Accordion Grading System. • MUFS.
Study Population:	Two hundred forty patients who will undergo standard of care pancreaticoduodenectomy and receive at least one dose of study treatment (PPI/placebo) at Washington University/Barnes-Jewish Hospital
Phase:	II
Description of Sites / Facilities Enrolling:	This study will take place at Washington University School of Medicine and associated hospitals/clinics.
Description of Study Intervention:	Immediately post-op, patients will be randomly assigned to one of the two standard of care approaches (“PPI” or “placebo”) on a 1:1 basis in a blinded fashion. Patients will be initiated on pantoprazole or a visually equivalent placebo once daily from Postoperative Day 1 and continued for 10 doses or until the day of discharge (whichever is earlier).
Study Duration:	39 months
Participant Duration:	90 days

SCHEMA

SCHEDULE OF ASSESSMENTS

Measure	Baseline ²	Pre-op Visit ³	Day of Surgery	Post-op Visit ⁴	90 Days Post-Op
Confirmation of surgical plan	X				
Patient consent			X ⁵		
Medical history		X			
Randomization			X ⁶		
Demographics captured from EMR ¹		X			
Drug/placebo administration			X ⁷		
Notes from surgery related hospitalization captured from EMR				X	
Information on surgical complications captured from EMR/HPB Whipple Database					X

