10.2 Sample Size Determination

For primary endpoint, our preliminary study showed that the rates of delayed gastric emptying in the control the PPI groups are 7% and 21%, respectively. 110 patients per group achieve 80.4% power to detect a 14% difference between two groups using the two-sided Fisher's Exact test at the significance level of 5%.

For the endpoint of surgical complication, our preliminary study showed that the rates in the control the PPI groups are 56% and 74%, respectively. 120 patients per group achieve 80.0% power to detect a 18% difference between two groups using the two-sided Fisher's Exact test at the significance level of 5%.

The preliminary data show approximate 27% of randomized patients did not receive at least one dose of study treatment (PPI/placebo) and were replaced. We will randomize 330 patients in order to obtain 80% power for these two endpoints and account for possible 27% drop-out. We estimate that 12 patients per month would be eligible for the trial and the enrollment could be complete within 36 months.

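### The adjusted logistic model in 10.5.2 has few events for its covariates: ordinary maximum likelihood would overstate the PPI odds ratio by roughly 8–14% (240 dosed) or 5–9% (330 randomised) under the planning rates, and a Firth fit corrects most of this cheaply

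*Combined protocol and SAP*

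**What the plan says.** Section 10.5.2 first lists group rates, an odds ratio and 95% confidence intervals for DGE. It then adds that "The logistic regression model will be considered to investigate the effect of PPIs accounting for the interested variables". The covariates are given as follows: "The interested variables include age, gender, body mass index, comorbidities, preoperative proton pump inhibitor usage, and surgical reconstruction method". The section does not say how the model is to be estimated, how comorbidities or reconstruction method are coded, or what happens under separation.

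The planning rates are in Section 10.2: "the rates of delayed gastric emptying in the control the PPI groups are 7% and 21%, respectively". The same section says "110 patients per group achieve 80.4% power to detect a 14% difference between two groups" for DGE by a two-sided Fisher's exact test, and "120 patients per group achieve 80.0% power to detect a 18% difference between two groups" for surgical complications. The larger requirement gives 240, and "We will randomize 330 patients in order to obtain 80% power for these two endpoints and account for possible 27% drop-out".

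The documents point to two different analysis sets. The Protocol Summary describes the study population as "Two hundred forty patients who will undergo standard of care pancreaticoduodenectomy and receive at least one dose of study treatment", and Section 5.1 makes a patient evaluable after one dose. Section 10.4.1 defines the efficacy set as everyone randomised.

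**The concern.** Treatment plus six variables is at least seven slopes, and more if comorbidities enter as separate indicators or reconstruction method has more than two levels. DGE is fairly uncommon, especially on placebo. With few events per coefficient, ordinary maximum-likelihood logistic regression tends to push a true non-zero log odds ratio away from zero, and some fits fail through separation. The adjusted odds ratio is a named estimate for the primary question, so its size matters to readers. If PPIs do raise the DGE rate as planned, it would on average be reported as too large.

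**Working it through.** **Inputs.** DGE rates of 7% and 21%, 110 and 120 per group, 27% undosed and 330 randomised (Section 10.2); 1:1 allocation (10.3); six covariates (10.5.2); DGE odds ratio of 2.355 in pancreaticoduodenectomy patients (Section 1.0).

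**The plan's own figures.** Exact two-sided Fisher power at 110 per group, 7% vs 21%, is 82.4% against 80.4% stated. The continuity-corrected formula returns 110 per group. At 120 per group, 56% vs 74%, exact power is 80.4% against 80.0% stated. 240/0.73 = 328.8, so 329 against 330. The planning inputs are therefore read correctly.

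**Events.**
- 240 dosed: 120 × 0.07 + 120 × 0.21 = 8.4 + 25.2 = 33.6. With seven slopes, 33.6/7 = 4.8 events per slope.
- 330 randomised, full rates: 165 × 0.07 + 165 × 0.21 = 11.55 + 34.65 = 46.2, or 6.6 per slope.
- 330 randomised, undosed PPI patients at the placebo rate: PPI rate 0.73 × 0.21 + 0.27 × 0.07 = 0.1722; events 165 × (0.07 + 0.1722) = 40.0, or 5.7 per slope.
- 240 dosed, odds ratio 2.355 on a 7% placebo rate: PPI rate 0.07 × 2.355/(0.93 + 0.07 × 2.355) = 0.1506; events 120 × (0.07 + 0.1506) = 26.5.

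**Bias with no covariates.** The true odds ratio is (0.21/0.79)/(0.07/0.93) = 3.53. By exact enumeration, the exponential of the mean estimated log odds ratio is 3.70 at 120 per arm (+4.8%) and 3.65 at 165 per arm (+3.3%).

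**Bias with covariates.** Simulation, 3,000–9,000 trials per setting. The covariate structure is assumed, because the documents give none: two continuous covariates, the rest binary at 10–50% prevalence, covariate log odds ratios 0, 0.3 or 0.5. Bias is measured against the true conditional odds ratio, as the exponential of the mean log-odds-ratio error. Non-converged maximum-likelihood (ML) fits were excluded. RMSE is the root mean squared error of the log odds ratio; where a setting was run more than once, the RMSE shown is from the largest run. Monte Carlo error is about 1 percentage point.

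| Setting | Events | Covariate columns | ML bias | Firth bias | RMSE, ML to Firth |
|---|---|---|---|---|---|
| 240, 7% vs 21% | 33.6 | 6 | +8% to +11% | −1.3% to +1.2% | 0.501 to 0.449 |
| 240, 7% vs 21% | 33.6 | 8 | +11% | −0.2% | 0.488 to 0.431 |
| 240, 7% vs 21% | 33.5 | 10 | +12% to +14% | −1.1% to +0.4% | 0.514 to 0.441 |
| 330, full rates | 46.2 | 6 | +7.0% | +0.4% | 0.408 to 0.379 |
| 330, full rates | 46.0 | 10 | +9.2% | 0.0% | 0.416 to 0.376 |
| 330, diluted | 40.0 | 6 | +5.3% | −0.2% | 0.400 to 0.374 |
| 240, OR 2.355 | 26.5 | 6 | +6.3% | −0.8% | 0.508 to 0.461 |
| 240, no effect | 16.8 | 6 | −1.8% | −1.6% | 0.584 to 0.523 |

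A second simulation with other assumptions (covariate log odds ratios 0.25, binary prevalence 15–50%, 4,000 trials) agrees. At 240 with 7, 9 and 12 coefficients, ML gives 3.80, 3.93 and 4.02 against 3.53 (+8%, +11%, +14%), and Firth gives 3.50–3.55.

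**Precision.** For the 7% vs 21% rows at 240, RMSE falls by 10%, 12% and 14% (for example 1 − 0.449/0.501 = 10%). For the 330 rows it falls by 7%, 10% and 6.5%.

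**Separation.** At 240, 2 of 9,000 ML fits failed with 6 columns, and 325 of 4,000 (8%) with 10.

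**Cost.** At 240, Wald power falls from 0.897 to 0.889 with 6 columns and from 0.904 to 0.893 with 10. Likelihood-ratio power falls from 0.905 to 0.894 and from 0.918 to 0.903; at odds ratio 2.355 it falls from 0.547 to 0.525. Mean fitted risk rises by 0.010–0.014 on an average of 0.14. Interval coverage is 94–96% for both methods.

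**The case against.** The case against acting is substantial, and most of it stands as a limit on the claim.

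- The model is only to be considered, after an unadjusted odds ratio, and the sample size rests on Fisher's test. A reader might infer that the primary test or the power is compromised; neither depends on this model.
- A reader might take 34 events and 8–14% as the plan's own position. The named efficacy set is all 330 randomised, where the range is 5–9%.
- A reader might blame the whole bias on the covariates. The unadjusted odds ratio already carries 4.8% at 240, so the six-column model adds only about 3–6 points. The top of the range needs 10 or more columns, which is assumed coding.
- The bias is small beside sampling error: ln 1.08 = 0.08 and ln 1.14 = 0.13, against a standard deviation near 0.5.
- A reader might infer that the analysis could manufacture harm from PPIs. With no effect there is no material log-odds-ratio bias, and Wald type I error is 4–5%.
- The plan names no estimator, so ordinary maximum likelihood is the default reading, not a stated choice. A Firth fit is already compatible with the text.

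What remains is that, under the planning alternative, both the bias and the RMSE of a named estimate can be reduced on the same data at little cost.

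**Conclusion.** The point holds as a cheap improvement of minor severity. Under the planning alternative, an ordinary maximum-likelihood fit overstates the PPI odds ratio by roughly 8–14% in 240 dosed patients or 5–9% in 330 randomised patients, of which about 3–5 points arise without any covariates. With the pancreaticoduodenectomy odds ratio of 2.355, the figure at 240 is about 6%. These ranges rest on assumed covariate distributions, effects and coding.

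Two stronger claims for the remedy do not hold. Firth does not remove all bias: it is near zero for the mean log odds ratio, but at 240 the arithmetic mean odds ratio is still about 10–13% too high (maximum likelihood 23–31%). Nor is it free, given the small loss of power and the shift in fitted risks.

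**What to change.** In Section 10.5.2:

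1. State that the adjusted model is a supportive estimate beside the unadjusted rates and odds ratio.
2. Fit it by Firth penalised likelihood with profile penalised-likelihood 95% confidence intervals.
3. Enter comorbidities as one pre-defined score or count, and state the coding of reconstruction method.
4. Name the analysis set, so that Sections 5.1 and 10.4.1 no longer point to different denominators.

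This is a few lines of text and a standard software option, with no new data beyond the covariates already named. It also gives finite estimates under separation. The downside is about 1–2 points of power for the adjusted test, and fitted risks about 1 percentage point too high unless the intercept is corrected before they are reported.

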10.5.3 Analysis of Secondary Endpoint(s)

Secondary endpoints include the incidence of surgical complication and marginal ulcer free survival. Surgical complication is defined by the Modified Accordion Grading System, coded as yes and no. The similar statistical approach to the primary endpoint will be employed. Any clinical diagnosis is used to define a marginal ulcer within 90 days after surgery. MUFS is defined as the days from the date of randomization to diagnosis of a marginal ulcer. The patients without marginal ulcer are censored at the date of last follow-up. The Kaplan-Meier method will be used to calculate the probability of marginal ulcer free survival at specific time points, e.g. 30 days, 90 days after surgery. The 95% CIs will be also provided. Differences between groups will be determined by log-rank tests. Cox

proportional-hazards models will be used to evaluate the effect of PPIs accounting for the other interested variables.

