5.3 Duration of Follow-up

Patients will be passively followed by review of the medical record for 90 days after surgery or until death, whichever occurs first.

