10.1.2 Secondary Objectives and Endpoints

1. Determine the effect of PPIs on the incidence of overall postoperative complications in the patients after pancreaticoduodenectomy.
2. Determine the marginal ulcer free survival (MUFS) within 90 days after surgery in the patients undergoing pancreaticoduodenectomy.

Secondary endpoints include: the incidence of surgical complication defined by the modified accordion grading system and MUFS.

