APPENDIX D: Modified Accordion Grading System

TABLE 5. Accordion Severity Classification of Postoperative Complications: Expanded Classification

1. Mild complication
Requires only minor invasive procedures that can be done at the bedside such as insertion of intravenous lines, urinary catheters, and nasogastric tubes, and drainage of wound infections. Physiotherapy and the following drugs are allowed-antiemetics, antipyretics, analgesics, diuretics, electrolytes, and physiotherapy.
2. Moderate complication
Requires pharmacologic treatment with drugs other than such allowed for minor complications, for instance antibiotics. Blood transfusions and total parenteral nutrition are also included.
3. Severe: invasive procedure without general anesthesia
Requires management by an endoscopic, interventional procedure or re-operation* without general anesthesia.
4. Severe: operation under general anesthesia
Requires management by an operation under general anesthesia.
5. Severe: organ system failure[†]
6. Death
Postoperative death.

*An example would be a wound reexploration under conscious sedation and/or local anesthetic.

[†]Such complications would normally be managed in an increased acuity setting but in some cases patients with complications of lower severity might also be admitted to an ICU.

ANNALS OF SURGERY

[The Accordion Severity Grading System of Surgical Complications](#)

Strasberg, Steven M.; Linehan, David C.; Hawkins, William G.
Annals of Surgery 250(2):177-186, August 2009.
doi: 10.1097/SLA.0b013e3181afde41

Accordion Severity Classification of Postoperative Complications: Expanded Classification

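### Marginal ulcer-free survival (MUFS) counts only ulcers and censors deaths, so the reported 30- and 90-day figures overstate the chance of being alive and ulcer-free

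*Combined protocol and SAP*

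**What the plan says.** The secondary objective in section 10.1.2 reads: "Determine the marginal ulcer free survival (MUFS) within 90 days after surgery in the patients undergoing pancreaticoduodenectomy". Section 10.5.3 gives the definition: "MUFS is defined as the days from the date of randomization to diagnosis of a marginal ulcer". For everyone else, "The patients without marginal ulcer are censored at the date of last follow-up".

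On the analysis, section 10.5.3 says "The Kaplan-Meier method will be used to calculate the probability of marginal ulcer free survival at specific time points", with 30 and 90 days as examples, and "Differences between groups will be determined by log-rank tests". Cox models are added for adjusted effects.

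Section 5.3 sets the length of follow-up: "Patients will be passively followed by review of the medical record for 90 days after surgery or until death, whichever occurs first".

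Death is foreseen elsewhere in the document. Grade 6 of the complication scale in Appendix D is "Postoperative death", Appendix E lists death among the expected post-surgical events, and the monitoring table in Appendix F has columns for vital status and cause of death. The objectives table in section 2.0 has complication grades 1 to 6 tabulated by arm. The same table justifies MUFS by the treatment and diagnosis of ulcers and does not mention death.

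**The concern.** An endpoint called ulcer-free survival is normally read as the chance of being alive without an ulcer. Under the written rules a death never lowers the curve. The name promises one quantity and the definition delivers another, and nothing elsewhere in the document makes death a MUFS event or a competing event.

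At stake is the percentage that will be reported and how it will be read. A 90-day MUFS close to 100% in each arm could be published as a survival result although it takes no account of patients who died after the operation. An arm difference in deaths would be missing from the one endpoint whose name includes survival.

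**Working it through.** The plan states no expected MUFS, event count or power, so there is no figure of its own to reproduce. The check has three steps.

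**1. The rules side by side**

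| Element | Source | Content |
|---|---|---|
| Event | 10.5.3 | ulcer diagnosis only |
| Censoring | 10.5.3 | all patients without an ulcer, at last follow-up |
| End of follow-up | 5.3 | day 90 or death, whichever is first |
| Estimator | 10.5.3 | Kaplan-Meier at, for example, 30 and 90 days |

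For a patient who dies ulcer-free, last follow-up can be no later than death, so that patient is censored. Section 10.5.3 does not mention death; this follows from reading it with section 5.3.

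**2. Size of the discrepancy at 90 days**

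Let u be the 90-day cumulative incidence of ulcer and d that of death without ulcer, with constant cause-specific hazards.

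- Alive and ulcer-free: S = 1 − u − d
- Total cumulative hazard: H = −ln(S); ulcer part: h = H × u/(u + d)
- Kaplan-Meier figure as planned: KM = exp(−h)
- Overstatement of ulcer-free survival: KM − S
- Overstatement of ulcer risk: (1 − KM) − u

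Inputs: section 1.0 cites ulcer incidences of 2.0% and 2.6% by type of operation, with median onset of 15.5 months. These are upper guides for 90 days, so 0.5% is shown as well. The death rate is an assumption, 1% to 5%.

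Example with u = 2% and d = 2%: S = 0.96; H = 0.04082; h = 0.04082 × 0.5 = 0.02041; KM = 0.9798. KM − S = 1.98 points; (1 − KM) − u = 0.020 points.

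| u | d | KM as planned | Alive and ulcer-free | Overstatement (points) | Ulcer risk excess (points) |
|---|---|---|---|---|---|
| 0.5% | 1% | 99.5% | 98.5% | 1.00 | 0.003 |
| 0.5% | 5% | 99.5% | 94.5% | 4.99 | 0.013 |
| 2.0% | 1% | 98.0% | 97.0% | 0.99 | 0.010 |
| 2.0% | 2% | 98.0% | 96.0% | 1.98 | 0.020 |
| 2.0% | 3% | 98.0% | 95.0% | 2.97 | 0.031 |
| 2.0% | 5% | 98.0% | 93.0% | 4.95 | 0.052 |
| 2.6% | 5% | 97.3% | 92.4% | 4.93 | 0.068 |

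The overstatement is almost exactly the assumed death rate, whatever the ulcer rate. The excess in ulcer risk never reaches 0.07 points.

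**3. What a composite would consist of**

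If ulcer onset were exponential with the cited median, the share appearing by 3 months would be 1 − exp(−ln 2 × 3/15.5) = 12.6%. Multiplied by 2.0% to 2.6%, that is 0.25% to 0.33% of patients, or 0.6 to 0.8 ulcers in 240. Deaths at 1% to 5% of 240 are 2.4 to 12. Deaths would then make up between 2.4/(2.4 + 0.8) = 75% and 12/(12 + 0.6) = 95% of composite events.

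At the other extreme, if the whole 2.6% appeared within 90 days (6.24 ulcers in 240), the share would run from 2.4/8.64 = 28% to 12/18.24 = 66%. Late onset makes the first case the more likely, but its shape is assumed.

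**The case against.** The strongest reply is that the endpoint is simply time to ulcer under a loose name. Section 10.5.3 gives an explicit ulcer-only event and section 2.0 justifies the endpoint by ulcers. On that reading the arm comparison is sound: censoring at death in a log-rank or Cox analysis gives a cause-specific comparison of ulcer hazards, which is a legitimate target. This stands, and it favours renaming over redefining. It does not rescue the percentage that is to be reported as ulcer-free survival.

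Four stronger readings are tempting, and the documents do not support them:

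- *The dead stay at risk or are scored ulcer-free to day 90.* A censored patient leaves the risk set. What Kaplan-Meier assumes is that the later ulcer risk of censored patients would match that of patients still followed.
- *Ulcer incidence will be materially biased.* In principle one minus Kaplan-Meier is not the cumulative incidence when deaths compete, but the table puts the difference below 0.07 points.
- *An excess of deaths in one arm would be hidden from the trial.* It would be absent from MUFS only. Section 2.0 tabulates complication grades 1 to 6 by arm, and grade 6 is death.
- *The endpoint must become ulcer or death.* By step 3 such a composite could be largely a mortality endpoint, while section 2.0 points to an ulcer-specific question.

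**Conclusion.** The concern holds as a mismatch between name and definition that produces a misleading reported figure. Followed exactly, the plan yields 30- and 90-day figures labelled ulcer-free survival that deaths cannot lower. At 90 days they exceed the true probability of being alive and ulcer-free by about the death rate, or 1 to 5 points at an assumed 1% to 5%.

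The mismatch itself rests on no assumption; it follows from sections 10.5.3 and 5.3. The size rests on a death rate that the documents do not give. The constant-hazard form matters little at such low rates, and the exponential onset affects only the expected make-up of a composite.

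The consequence is limited. MUFS is a secondary endpoint with no power statement and few expected events, and the primary endpoint and the sample size do not depend on it. It should be corrected before analysis.

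**What to change.** In section 10.5.3, make the name and the event agree.

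- **Proportionate change.** Rename the endpoint 'time to marginal ulcer'. Report cumulative incidence per arm at 30 and 90 days with 95% confidence intervals, treating death without ulcer as a competing event (Aalen-Johansen estimator). Keep the log-rank and Cox analyses and describe them as cause-specific comparisons.
- **If a figure labelled ulcer-free survival is still wanted.** Count the first of ulcer diagnosis or death from any cause within 90 days, and censor only patients last known alive and ulcer-free. Show ulcers and deaths separately beside it, since deaths would probably form most of the events.

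The same name should be used in the Protocol Summary, sections 2.0, 5.1 and 10.1.2, and Appendix F.

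The cost is mainly wording. Vital status and cause of death are already tabulated in Appendix F, and the follow-up rule in section 5.3 needs the date of death. A true survival figure will look slightly less favourable. Both options depend on deaths being found by passive record review with no mandated visits, so section 10.5.3 should say how vital status at day 90 is established and how patients with unknown status are handled.

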According to a meta-analysis performed by Butler et al., PPIs are frequently used in patients undergoing pancreaticoduodenectomy, with 86% of surgeons prescribing them after pancreatic resection. Forty-six percent of surgeons continue their patients on these medications for life, while 25% give the prescriptions for 30 days postoperatively (18). The main indication for their use is to reduce the occurrence of postoperative marginal ulcers, a morbid complication of pancreaticoduodenectomy with a reported average incidence of 2.0% after pylorus-preserving pancreaticoduodenectomy and 2.6% after classic pancreaticoduodenectomy (18). However, the onset of marginal ulcers is often delayed, with the median time for development of marginal ulceration after pancreaticoduodenectomy being 15.5 months (18, 19).

PPIs have been effective in decreasing the incidence of postoperative marginal ulcers. The development of marginal ulcers is driven by two mechanisms:

1. Local inflammation, ischemic changes at the anastomotic site, foreign bodies (sutures, staples), which is the primary mechanism in the immediate postoperative period, and
2. The direct effect of gastric acid on jejunal mucosa which is the primary mechanism in later periods (19).

Increased gastric acid production, low gastric pH, and prolonged duration of low pH are associated with marginal ulcers (20). However, the recommendations regarding the timing and duration of their use after pancreaticoduodenectomy remain unclear and need to be defined.

In our recently completed retrospective chart review (IRB ID: 201711053), we evaluated the

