impact of gastric acid inhibitors (PPIs and H2Receptor antagonists) on postoperative outcomes following pancreatic resection i.e., pancreaticoduodenectomy, distal pancreatectomy, and completion pancreatectomy. H2Receptor antagonists are associated with postoperative delirium and, therefore, are not frequently used (21). In our study cohort, 66.5% of patients were administered gastric acid inhibitors postoperatively, with the majority of these patients (76.4%) receiving PPIs. Comparative analysis of postoperative complications in patients who received acid suppression and those who did not showed a significantly higher incidence of all complications (73.8 % vs 56.4%) ($p=0.003$), delayed gastric emptying (20.9% vs 6.4%) ($p=0.002$), postoperative hemorrhage (23% vs 8.5%) ($p=0.003$), failure to thrive (4.3% vs 0%) ($p=0.042$), and all infectious complications (23.5% vs 11.7%) ($p=0.018$) in the acid suppression group. Multivariate logistic regression analysis demonstrated a significant association between the use of gastric acid inhibitors and the incidence of all postoperative complications (Odds Ratio=2.176), including delayed gastric emptying (Odds Ratio=3.7148) in the patients undergoing pancreatic resection. Our analysis also showed a significant association between the use of these agents and postoperative complications (Odds Ratio=2.469) and delayed gastric emptying (Odds Ratio=2.355) in patients that underwent pancreaticoduodenectomy.

Our results highlight the need for promoting pharmacovigilance when it comes to prescribing gastric acid inhibitors after pancreatectomies. Utilizing PPIs in the immediate postoperative period as prophylaxis against marginal ulcers that generally occur months after surgery at the cost of an increase in postoperative complications such as delayed gastric emptying is not in the patient's best interest, and therefore, should be avoided. The purpose of this study is to prospectively determine the effects of administering PPIs following pancreaticoduodenectomy on postoperative outcomes. The findings of this study will help in avoiding the widespread use of PPIs during the immediate postoperative period following pancreatic surgery.

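### Section 10.5.3 gives no interval for the between-arm difference in 90-day marginal ulcer risk, and the log-rank test and Cox model it relies on will probably yield no usable estimate of it

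*Combined protocol and SAP*

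**What the plan says.** Section 10.5.3 defines marginal ulcer-free survival (MUFS) from randomization to diagnosis, with ulcer-free patients censored at last follow-up. On the window it says "Any clinical diagnosis is used to define a marginal ulcer within 90 days after surgery". It plans Kaplan-Meier probabilities at times such as 30 and 90 days and adds "The 95% CIs will be also provided", which in its place refers to those probabilities.

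Two analyses compare the arms. The first is "Differences between groups will be determined by log-rank tests". The second is Cox regression: "proportional-hazards models will be used to evaluate the effect of PPIs accounting for the other interested variables". The section gives no interval for the difference in 90-day risk, no expected number of ulcers, and no guidance on reading a null result. Section 10.2 sizes the trial for delayed gastric emptying (DGE) and surgical complications only.

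On follow-up, Section 5.3 says "Patients will be passively followed by review of the medical record for 90 days after surgery or until death, whichever occurs first". Section 1.0 cites an "average incidence of 2.0% after pylorus-preserving pancreaticoduodenectomy and 2.6% after classic pancreaticoduodenectomy", with "the median time for development of marginal ulceration after pancreaticoduodenectomy being 15.5 months". It also states the intended use: "The findings of this study will help in avoiding the widespread use of PPIs during the immediate postoperative period following pancreatic surgery".

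**The concern.** Section 1.0 names ulcer prevention as the main reason for giving PPIs after this operation and says they work for that purpose. Anyone who uses the trial to argue against early PPIs will therefore ask what happened to ulcers in the placebo arm. MUFS is the only endpoint dedicated to that question.

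The cited ulcers are few and mostly late, while observation stops at day 90. A handful of events is the likely yield. With so few, a log-rank p-value says almost nothing about how large an excess remains possible, and an adjusted Cox model may not produce an estimate at all. What is at stake is whether the report can show the reader how much ulcer harm the data leave open.

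**Working it through.** **Sample sizes.** Section 10.3 randomizes 330 at 1:1, so 165 per arm, which is the ITT set of Section 10.4.1. Section 10.2 needs 120 per arm for complications, and 240 / (1 − 0.27) = 329, which agrees with the planned 330. Both 165 and 120 are used below, because Section 5.1 calls only dosed patients evaluable. The plan states no power or event count for MUFS, so there is no figure of its own to reproduce for this endpoint.

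**90-day risk (assumption).** Take onset as exponential with median 15.5 months. Ninety days is 90 / 30.4375 = 2.96 months. The fraction of ulcers by day 90 is 1 − 2^(−2.96/15.5) = 0.124. Taking the cited incidence as the PPI-arm rate gives 0.124 × 2.0% = 0.25% and 0.124 × 2.6% = 0.32%.

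**Expected events with a five-fold placebo excess.** n × 6 × risk: 165 × 6 × 0.0025 = 2.5 and 165 × 6 × 0.0032 = 3.2 ulcers in the whole trial.

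**Smallest significant result.** With equal arms and rare events the log-rank chi-square is close to (x − y)² / (x + y), where x and y are the ulcer counts. A 3-0 split gives 9/3 = 3.0, p about 0.08. A 4-0 split gives 16/4 = 4.0, p about 0.046. So at least 4-0 is needed.

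**Miss rate.** Sum the binomial probabilities of all (x, y) with chi-square below 3.84, or with the excess on PPI. The 5% two-sided level is assumed, since Section 10.2 states it only for the two powered endpoints.

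| PPI-arm 90-day risk | True placebo risk | Miss, 165 per arm | Miss, 120 per arm |
|---|---|---|---|
| 0.25-0.32% | doubled | about 99% | above 99% |
| 0.25-0.32% | tripled | 95-98% | 98-99% |
| 0.25-0.32% | five-fold | 83-90% | 91-95% |
| 0.5% | five-fold | 69% | 80% |
| 1.0% | five-fold | 42% | 56% |
| 2.0% | five-fold | 10% | 21% |

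As a check, a simulation of the full log-rank test (exponential times, censoring at day 90, 6,000 runs) at 0.32% against 1.6% with 165 per arm gave a miss of 82.7%; the enumeration gives 83.2%.

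**Cox model.** The hazard ratio has no finite maximum-likelihood estimate when one arm has no ulcers. The chance of no ulcers on PPI at 165 per arm is (1 − 0.0032)^165 = 59% to (1 − 0.0025)^165 = 66%.

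**What an interval would show, free of any onset model.** The Wilson upper limit for 0 of n is 3.84 / (n + 3.84): 3.84/168.84 = 2.3% and 3.84/123.84 = 3.1%. With no ulcers in either arm, the Newcombe 95% upper limit for placebo minus PPI equals that value: +2.3 points (165 per arm) or +3.1 points (120 per arm). At a non-significant 3-0 split against placebo the interval runs from −0.8 to +5.2 points (165 per arm) or −1.0 to +7.1 points (120 per arm).

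**The case against.** The strongest case against this point is that MUFS is an unpowered secondary endpoint in a phase II trial, and low power for a rare event is a limitation to report rather than an error. Section 10.1.2 even words the objective as determining MUFS, not the effect of PPIs on it, and the Kaplan-Meier intervals would show the imprecision within each arm. That stands as far as power goes, and no larger trial is asked for. It does not answer the missing between-arm estimate: Section 10.5.3 does plan a group comparison, and two arm-level intervals are not an interval for their difference.

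The exponential model is also open to challenge. Section 1.0 describes separate early and late mechanisms, with acid primary in the later period, so a constant hazard may understate early risk. Treatment lasts at most 10 doses, so a five-fold early excess may be unlikely. Both remarks are fair. The five-fold ratio only illustrates insensitivity, and the 0-0 limits do not depend on either assumption.

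Three stronger readings are tempting, and the documents do not support them:

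- A reader might take 83% as a minimum miss rate. It is not a floor; the table shows the five-fold miss falling to 10% at a PPI-arm risk of 2.0% with 165 per arm.
- A reader might say that the log-rank test is the only planned comparison. The Cox model is planned too, though with about three events it would be no more informative.
- A reader might infer that a non-significant result will be presented as proof that withholding PPIs is harmless. No section says so, and the Section 1.0 argument against early use rests on ulcers occurring late, not on a null MUFS test.

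**Conclusion.** The point holds as a gap in the analysis method. Section 10.5.3 offers a p-value and a hazard ratio that may not exist, and no estimate showing how large a 90-day ulcer excess remains compatible with the data.

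The miss rates of 83-90% (165 per arm) and 91-95% (120 per arm) for a five-fold excess are conditional. They assume that the cited incidence applies to the PPI arm, exponential onset at the cited median, a two-sided 5% test and complete 90-day follow-up. The upper limits of 2.3 and 3.1 points with no ulcers observed need only the sample size and complete 90-day status. For scale, they are close to or above the whole 2.0-2.6% incidence cited in Section 1.0, although that incidence is not stated to be a 90-day figure.

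The analyses of DGE and of complications are untouched. The change should be made, but it concerns one secondary endpoint and how its result is reported.

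**What to change.** In Section 10.5.3, make the between-arm summary for marginal ulcers the difference (placebo minus PPI) in 90-day risk with a two-sided 95% interval suited to rare events:

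- If 90-day ulcer status is complete, use the Newcombe or Miettinen-Nurminen interval.
- If patients are censored before day 90, use a Newcombe-type interval built on the Kaplan-Meier estimates with effective sample sizes. Say in advance what sample size is used for an arm with no ulcers, where the Greenwood variance is zero.

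Keep the log-rank p-value as descriptive. Add two sentences: any statement about ulcer safety rests on the upper limit of this interval, and a non-significant test will not be read as absence of an increase. State that conclusions on DGE and complications do not depend on it.

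The cost is SAP wording and one extra computed interval, with no new patients or data. The downside is a less favourable ulcer statement that will probably be inconclusive.
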